## **Summary**

Compared to healthy people without migraine, migraine is associated with alterations in brain structure and function. This is a prospective, longitudinal, open-label study that will investigate brain magnetic resonance imaging changes amongst individuals with migraine following treatment with erenumab.

The Specific Aims of this study are to:

- 1. Identify changes in brain function and structure that correlate with response to erenumab.**
- 2. Develop models using imaging data to predict which patients will respond to erenumab.**  
Pre-treatment and early post-treatment imaging data will be used separately for predictive modeling.

The study will include 50 subjects with migraine aged 18-65 years who have 6-25 migraine days per month at baseline. Following a 4-week run-in phase, subjects will be treated twice with once monthly subcutaneous injections of erenumab 140 mg. Questionnaires, structured interviews, cognitive tests, quantitative sensory testing and brain imaging will be performed prior to and following erenumab treatment. These data will be collected at early time points after the first treatment as well as at eight weeks following the first treatment to allow for identification of early and late effects of erenumab on clinical, physiologic, and imaging outcomes and to determine if early physiologic and imaging outcomes predict clinical outcomes at eight weeks. Physiologic and imaging data will be compared to already collected data from healthy controls so as to interpret changes that are seen following treatment with erenumab.

The primary hypothesis is that improvements in migraine patterns associated with erenumab treatment will be associated with “normalization” of brain function. Secondarily, it is hypothesized that improvements in migraine patterns associated with erenumab treatment will be associated with “normalization” of brain structure, pain thresholds, and cognitive performance. Finally, it is hypothesized that exploratory analyses will demonstrate that there are early changes in brain function following the first treatment with erenumab and that these early changes will be predictive of longer-term clinical responsiveness to erenumab.

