## **Published Work and Preliminary Data**

Our team has performed multiple studies that are directly relevant to the goals of this project and serve as evidence of our ability to successfully conduct this study. We have completed studies comparing noxious heat-induced brain activation patterns in people with migraine vs. healthy controls. (13) These studies showed that migraineurs have greater pain-induced activation in several brain regions, many of which participate in cognitive aspects of pain processing. For several of these regions, the extent of greater activation correlated with the frequency of headaches, serving as strong evidence for a direct relationship between having migraine and greater activation of these pain-processing brain regions and at least suggesting that reductions in headache frequency would correlate with reductions in pain-induced activation. Our resting-state functional connectivity studies have investigated functional connectivity of affective-emotional pain processing regions and of descending pain modulatory brainstem regions. (14, 15) These studies demonstrated that migraineurs have atypical functional connectivity and the extent of atypical connectivity correlates with measures of migraine disease burden such as number of years with migraine and allodynia symptoms. Our structural MRI studies have shown migraineurs to have atypical structure of the brainstem and abnormal cortical thinning with age, aberrant correlations between brain cortical thickness and cutaneous pain thresholds, atypical cortical thickness correlations, and abnormal white matter tract integrity. (16-18) Furthermore, our work has shown migraineurs with interictal photosensitivity to have thicker cerebral cortex in parieto-occipital and fronto-parietal regions. (19) Finally, our machine-learning multivariate pattern analyses have yielded migraine classifiers that use brain structural data to differentiate the brain of an individual chronic migraineur from that of a healthy control (see Figure 1) or episodic migraineur (see Figure 2) with high accuracy (American Headache Society Wolff Award winning paper). (20) Our classifiers based on resting state functional connectivity data differentiate the brain of an individual migraineur from a healthy control with high accuracy (American Academy of Neurology Harold Wolff – John Graham Award winning research, see Figure 3). (20, 21) In addition, we developed a decision support system using multi-modality imaging data to interrogate the utility of combining structural and functional imaging data for migraine patient discrimination and the accuracy of such discrimination. (see Figure 4) (22) Results showed better classification accuracy when combining structural and functional data than using either data type alone.

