**Table 1- Study Flow.**

	Run in Phase (time: -4 wks)	Baseline (time: 0)	First Follow-up (time: 2 wks)	Second Follow-up (time: 4 wks)	Third Follow-up (time: 8 wks)	Fourth Follow-up (time: 12 wks)
Determine Eligibility	X	X				
Questionnaires	X	X	X	X	X	X
QST		X	X		X	
MR Imaging		X	X		X	
Cognitive Testing		X	X		X	
Vital Signs		X	X	X	X	X
Urine Pregnancy Test		X		X		
Erenumab Treatment		X		X		
Headache Diary	X	X	X	X	X	X

**Participants:** Up to 67 adult patients who are at least 18 years of age but younger than 66 years of age with high frequency episodic migraine or chronic migraine with and/or without aura will be enrolled into the run-in phase of this study at Mayo Clinic Arizona. Enrollment will stop once 50 subjects provide headache diary during the run-in phase that meets eligibility criteria (i.e. documented 6-25 migraine days per 28 days). Previously collected data of healthy control subjects (n=50) will be used for data comparison. Exclusion and inclusion criteria will be modeled after those used in the phase 2 and 3 trials of erenumab for the prevention of migraine. (6, 8) In addition, patients who have contraindications to MRI (e.g. metal implants, aneurysm clips, severe claustrophobia) will be excluded from study participation. Potential participants will be excluded if they have active chronic pain conditions other than migraine (e.g. chronic pelvic pain) or acute pain conditions (e.g. recent surgery). Potential participants who have sensory disorders that might affect the perception of cutaneous thermal stimuli will also be excluded (e.g. peripheral neuropathy).

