#### Analysis Plans

*Specific Aim #1 (i.e. identify changes in brain structure and function that correlate with response to erenumab):* Pre-treatment and post-treatment MRI data will be used for within and between subject

comparisons. Within subject analyses will compare baseline brain activation and perfusion patterns and functional connectivity patterns pre-treatment to post-treatment. Between subject group analyses will compare post-treatment MRI data in erenumab responders to non-responders.

Similar comparisons will be made for pre- and post-treatment pain thresholds (i.e. results of quantitative sensory testing) and cognitive testing.

So as to help with the interpretation of differences between responders and non-responders, MRI data from erenumab-treated patients will be compared to healthy non-migraine control data that we have already collected during the conduction of previous studies, when available (although we have plenty of data for the majority of analyses, we have limited ASL data and no n-back data from healthy controls). Differences in brain structure and function of migraine patients prior to erenumab treatment compared to healthy controls will be identified. Results of this analysis will determine alterations of brain structure and functions in migraine patients compared to healthy controls. Areas where migraine patients show altered structure and function will be used as regions of interest (ROIs) to assess the longitudinal, within-group changes of erenumab responders and non-responders.

Although multiple analyses are planned using functional, structural, and perfusion data, the primary analysis for specific aim #1 will be the comparison of pre-treatment pain-induced regional activation strength vs. post-treatment pain-induced regional activation strength in erenumab responders and separately in erenumab non-responders.

Post-treatment changes in other measures of brain function as well as measures of brain perfusion, brain structure, cutaneous pain thresholds and cognitive function in those responding to erenumab and in those not responding will be explored.

Two-tailed T-Tests or Mann-Whitney U tests will be used to perform group comparisons on demographic and cognitive measures and on pain threshold data. Neuroimaging data will be analyzed using general linear model designs. Within-group changes on cognitive measures, sensory testing and neuroimaging data will be assessed by applying a general linear mixed model design.

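### Pain thresholds and cognitive scores are compared between non-randomised groups with tests that cannot adjust for age or sex, and no matching or covariates are stated for the healthy-control comparison

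*Combined protocol and SAP*

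**What the plan says.** Under Specific Aim #1, the Analysis Plans section first describes pre/post comparisons and a comparison of responders with non-responders on MRI data. It then adds: "Similar comparisons will be made for pre- and post-treatment pain thresholds (i.e. results of quantitative sensory testing) and cognitive testing". Healthy controls come in after that, for imaging: "MRI data from erenumab-treated patients will be compared to healthy non-migraine control data that we have already collected". The same sentence concedes that "we have limited ASL data and no n-back data from healthy controls".

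The Summary is wider: "Physiologic and imaging data will be compared to already collected data from healthy controls". The Participants paragraph under Methods gives the source and number: "Previously collected data of healthy control subjects (n=50) will be used for data comparison".

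The method for the non-imaging outcomes is: "Two-tailed T-Tests or Mann-Whitney U tests will be used to perform group comparisons on demographic and cognitive measures and on pain threshold data". Imaging data go to general linear models with no covariates listed, and within-group changes go to a mixed model. The patient-control imaging contrast has a further use: "Areas where migraine patients show altered structure and function will be used as regions of interest (ROIs" in the longitudinal analysis of responders and non-responders.

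Nowhere does the document give the controls' age, sex, scanner or sequences, or a matching rule.

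**The concern.** A two-sample t-test or Mann-Whitney test is safe against confounding when randomisation makes the groups comparable. Here nothing does. Response is observed after treatment, and the controls come from earlier studies. Patients may be anywhere from 18 to 65 years old, so there is ample room for the groups to differ in age.

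Age is a foreseeable confounder on the team's own evidence: the Published Work section reports "abnormal cortical thinning with age" in migraine, and correlations between cortical thickness and cutaneous pain thresholds.

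Three things are at stake:

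- the reading of threshold and cognitive differences between groups;
- the choice of regions followed over time, since an age, sex, head-size or scanner difference in the imaging contrast can enter as a migraine alteration;
- the meaning of normalization, which the Summary hypothesises for structure, thresholds and cognition and which needs a sound reference for normal.

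**Working it through.** **Which comparisons the named tests can cover**

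| Outcome | Responders v non-responders | Patients v controls |
|---|---|---|
| Heat pain thresholds | Yes (Analysis Plans) | Yes, by the Summary's reference to physiologic data; the Analysis Plans section names MRI data only |
| Trails A and B | Yes | Not stated; control data not mentioned |
| N-back | Yes | Not possible; no control data |
| MRI measures | General linear model, covariates unlisted | General linear model, covariates unlisted; selects the regions of interest |

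The covariate-free tests therefore apply to thresholds and cognition between response groups and, on the Summary's wording, to thresholds against controls.

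**The plan's own figure.** The only power statement (88%, 21 per group, difference 0.1, SD 0.1, type I error 0.05) reproduces as 88.5% with a two-sided two-sample t-test. It concerns BOLD signal and is not in dispute here.

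**Size of the possible distortion**

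Inputs from the document:

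- 50 controls.
- 50 patients less 15% with incomplete data: 50 × 0.85 = 42.5, so about 42.
- 21 per response group (Sample Size).

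Inputs assumed, because the document gives none:

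- a covariate imbalance g between groups, in SD units;
- a within-group correlation r between covariate and outcome.

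With no true group effect, the spurious difference in outcome SDs is r × g. The standard error is √(1/n₁ + 1/n₂), and the non-centrality is the ratio of the two. The rejection rate comes from the non-central t at the two-sided 5% critical value.

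For 42 v 50 at g = 0.5:

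- Standard error = √(1/42 + 1/50) = 0.209; 90 degrees of freedom; critical value 1.987.
- r = 0.3: 0.15 / 0.209 = 0.72, rejection rate 10.9%.
- r = 0.5: 0.25 / 0.209 = 1.19, rejection rate 21.9%.

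Range over g for 42 v 50:

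| Imbalance g | r = 0.3 | r = 0.5 |
|---|---|---|
| 0 | 5% | 5% |
| 0.25 SD | 6.5% | 9.1% |
| 0.5 SD | 10.9% | 21.9% |
| 0.75 SD | 18.6% | 42.6% |
| 1.0 SD | 29.4% | 65.7% |

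With all 50 patients, g = 0.5 gives 11.5% to 23.6%.

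For responders v non-responders, 21 v 21 at g = 0.5, the standard error is √(2/21) = 0.309 and the non-centralities are 0.49 and 0.81. The same formula gives 7.6% to 12.4%. The bias in SD units is unchanged; the smaller groups only make it less likely to cross the threshold.

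**Effect of adjustment.** In a simulation of 20,000 runs per scenario (42 v 50; g = 0, 0.5, 1.0; r = 0.3, 0.5), a linear model containing the covariate rejected 4.6% to 5.2% of the time in all six scenarios. The simulated covariate effect was linear and the same in both groups.

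**The case against.** The strongest reply is that the sentence on t and Mann-Whitney tests never mentions controls. Threshold and cognitive comparisons are introduced before controls appear, and the control comparison in that section is of MRI data, offered as an aid to interpretation. This stands, and it rules out several stronger readings that a reader might infer:

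- *The controls are unmatched.* The document is silent on matching; silence shows only that it is unspecified.
- *Cognition will be compared with controls.* N-back cannot be, and no control Trails data are mentioned.
- *Scanner differences distort thresholds or cognitive scores.* Those come from a thermode, worksheets and a laptop. Scanner matters only for MRI.
- *The t-tests define the regions of interest.* Those come from imaging models, which can hold covariates; the plan just does not list them. On its own that would be missing detail.
- *The primary analysis is biased.* It compares each patient before and after treatment on one scanner. Sex and head size are essentially fixed and age barely moves over eight weeks. A badly chosen region may dilute or mislead, but does not create a pre/post change. The event-related analysis is also described as whole-brain, and connectivity uses 33 pain-processing regions.

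It is also fair that the imbalance and correlation are assumed, that single-test rates do not carry over to imaging analyses with multiplicity correction, and that the planned demographic comparison might reveal an imbalance. Revealing an imbalance is not adjusting for it. The reply leaves intact that the named tests admit no covariates while the groups, whichever are meant, are not randomised.

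**Conclusion.** The concern holds in a limited form. For between-group comparisons of thresholds and cognitive scores the plan specifies a method that cannot adjust, where adjustment is cheap and foreseeably needed. For the patient-control imaging contrast it states neither matching nor covariates, although that contrast feeds region selection.

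The illustrative size is a false-positive rate of about 11% to 22% against a nominal 5% (42 v 50, 0.5 SD imbalance, correlation 0.3 to 0.5). It rests wholly on those two assumptions; with no imbalance the rate is 5%. The risk is to the threshold and cognitive group comparisons, to region selection and to the reading of normalization. This is a change that should be made, but it does not undermine the primary analysis.

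**What to change.** Before the contrasts are run, so that covariates are not chosen after seeing them:

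1. Replace the t and Mann-Whitney comparisons of thresholds and cognitive scores with linear models including age and sex, on ranks where the outcome is skewed. Keep the simple tests for demographics.
2. Name the groups compared for each outcome, and reconcile the Summary with the Analysis Plans section on whether thresholds are compared with controls.
3. Put age and sex in the patient-control imaging models that select the regions of interest, adding intracranial volume for regional volumes and surface areas.
4. Report the controls' age, sex, scanner and sequences, with a sensitivity analysis limited to controls whose scanner and sequences match those under Imaging Data Plans.

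For patients, age and sex are already on the Demographics form; the control equivalents must be confirmed. The cost is two or three degrees of freedom and a linear-age assumption. Because the team reports an atypical relation between age and cortical thickness in migraine, an age-by-group check is sensible for thickness. How many controls match on scanner is unknown, which is why that restriction is proposed as a sensitivity analysis.

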#### Baseline (first treatment) Visit

Patients will return for a baseline visit after 4 weeks (i.e. 28 days +/- 3 days since start of run-in phase) of prospective headache diary collection. Diary compliance and eligibility for study inclusion will be assessed. Patients who still meet eligibility criteria will have measurement of vital signs and urine pregnancy testing will be conducted for women of childbearing potential. Levels of depression and anxiety will be measured using the Beck Depression Inventory and State-Trait Anxiety Inventory, respectively. Functional disability will be assessed with the Migraine Disability Assessment (MIDAS) and the Migraine Functional Impairment Questionnaire (MFIQ). Symptoms of cutaneous allodynia will be assessed using the Allodynia Symptom Checklist 12. Symptoms of cognitive dysfunction associated with migraine will be assessed using the Mig-Scog Questionnaire. (24, 25) Patients will undergo

quantitative sensory testing (QST) for determination of heat pain thresholds and the temperature that results in moderate intensity heat pain. (13, 26, 27) To assess cognitive function, patients will complete two attention tasks; a computer version of the n-back task and Trails A and B.

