### Trails A and B

Subjects will complete the standardized worksheets of Trails A and B. On Trails A, subjects are asked to connect consecutive numbers from 1-25. On Trails B, subjects are asked to alternate between

connecting numbers and letters. (i.e., 1-A-2-B-3-C, and so forth) Both tests are measuring attention and processing speed. For both tests, number of errors are recorded as well as the number of seconds required to complete each task.

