classic imputation methods commonly used in clinical trials will be adopted.(6) Specifically, for months with 20-27 days of dairy data, the values for missing entries will be imputed by prorating scores of 28-day post-treatment periods. That is, monthly migraine frequency can be calculated as the ratio of number of observed migraine days to number of observed days multiplied by 28. For months with less than 10 days of dairy data, monthly migraine frequency will be estimated by the substitution of the patient's previous 28-day period score, multiplied by the ratio of the mean for all patients in the same period to the mean for all patients in the previous period. For post-treatment periods with 10-19 days of diary data, scores will be estimated using a mean of both methods.

**Follow up visits One through Four (see table 1):** Four follow-up visits will be scheduled: at weeks 2, 4, 8 and 12 post-initial treatment with erenumab (week 2 = 14 days +/- 2 days since first visit; week 4 = 28 days +3 days since first visit; week 8 = 56 days +/- 3 days since first visit; week 12 = 84 days +/- 5 days since first visit). The early follow-up at 2 weeks will be utilized for repeat QST, brain imaging and cognitive testing so that data are available for investigating early markers/predictors of treatment response. A second treatment with erenumab will occur during the 4-week visit. Imaging, QST and neurocognitive testing will be repeated during the 8-week visit, allowing for determination of biomarkers for treatment response that might not have been found at the early time-point of 2 weeks and that can be correlated with clinical measures of treatment response (i.e. changes in migraine day frequency). The 12-week visit will allow for further assessment of safety and efficacy.

**Acute Migraine Therapy:** Patients will be allowed to use acute headache treatments including migraine-specific medication (e.g. triptans, ergotamine derivatives) and NSAIDs during the study.

**Other Migraine Preventive Therapy:** Patients will be allowed to use two or fewer migraine preventive therapies in addition to erenumab as long as the dose has been stable for at least 2 months before the start of the run-in phase. Changes to the dose of such treatments will not be allowed during this study unless necessary due to safety issues or lack of tolerability.

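### The within-group tests of cognitive change cannot separate practice from treatment, and the plan does not name the responder versus non-responder contrast in change that would

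*Combined protocol and SAP*

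**What the plan says.** The Summary gives a secondary hypothesis that "improvements in migraine patterns associated with erenumab treatment will be associated with “normalization” of brain structure, pain thresholds, and cognitive performance". Under the baseline visit, "patients will complete two attention tasks; a computer version of the n-back task and Trails A and B". The follow-up visits paragraph repeats the tests twice: "The early follow-up at 2 weeks will be utilized for repeat QST, brain imaging and cognitive testing", and "Imaging, QST and neurocognitive testing will be repeated during the 8-week visit". Table 1 agrees, with cognitive testing at weeks 0, 2 and 8.

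For Specific Aim #1, Analysis Plans describes three things that bear on cognition:

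- **Within-group change.** "Within-group changes on cognitive measures, sensory testing and neuroimaging data will be assessed by applying a general linear mixed model design". Cognitive change is to be explored in responders and in non-responders. No group-by-time term is named.
- **Between-group comparison.** Post-treatment MRI data are compared between responders and non-responders, and similar comparisons are promised for cognitive testing. Two-tailed t-tests or Mann-Whitney tests are named for group comparisons on cognitive measures, without saying whether baseline, post-treatment or change scores are tested.
- **Healthy controls.** These are previously collected data, used where available. The plan adds that "we have limited ASL data and no n-back data from healthy controls".

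**The concern.** People can do better on an attention task at a second or third sitting without any treatment. A faster Trails time or more n-back hits at week 8 is also the direction in which the hypothesis points. A pre-post test within one group attributes the whole shift to the treatment period.

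Two readings could then go wrong. One is that a significant change within responders is taken as a drug-related cognitive gain. The other is that a significant result in responders beside a non-significant one in non-responders is taken as evidence of association with response, although the two groups were never compared directly on change.

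Separately, normalization implies movement toward a healthy reference. For n-back the study holds no such reference.

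**Working it through.** **Inputs from the protocol.** Sample Size expects at least 21 responders and 21 non-responders (50 × 0.85 = 42.5, about half responding) and a type I error of 0.05. I take the tests as two-sided, in line with the two-tailed tests in Analysis Plans.

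**Assumed.** The protocol gives no practice effect. I use a mean shift d of 0.2, 0.3 or 0.5 SD of change, equal in both groups, with no drug effect.

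**The plan's own figure.** The 88% power in Sample Size is for a BOLD difference of 0.1% with SD 0.1. A two-sided two-sample t-test at 0.1/0.1 = 1.0 SD with 21 per group gives 88.5%, so the figure reproduces. It does not concern cognition, for which no figure is stated.

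**Step 1: within-group test at n = 21.** The rejection probability comes from the noncentral t with 20 df and noncentrality d√21.

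**Step 2: significant in responders, not in non-responders.** The two groups are different patients, so with rejection probability p in each, the chance is p(1 − p). Its maximum is 25%, at p = 0.5.

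| d | d√21 | p (step 1) | p(1 − p) (step 2) |
|---|---|---|---|
| 0.2 | 0.917 | 14.1% | 0.141 × 0.859 = 12% |
| 0.3 | 1.375 | 25.8% | 0.258 × 0.742 = 19% |
| 0.5 | 2.291 | 58.7% | 0.587 × 0.413 = 24% |

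The result depends on the unit. If d is instead in SDs of the score at one visit, divide it by √(2(1 − ρ)), where ρ is the pre-post correlation. At ρ = 0.5 nothing changes. At ρ = 0.7 step 1 becomes 20%, 39% and 80%.

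**Step 3: direct contrast of change, 21 v 21.** The expected difference is d − d = 0, so the test keeps its level. Simulation (20,000 trials at each of d = 0, 0.3, 0.5 and 0.8) rejected in 4.8% to 5.3%.

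**Step 4: comparison of post-treatment scores only, 21 v 21.** Common practice cancels here too, but a pre-existing difference δ between the groups stays in full. The noncentrality is δ√(21/2). For an assumed stable δ of 0.3 or 0.5 SD of the score, this is 0.972 or 1.620, and the test is significant in 16% or 35% of trials with no drug effect.

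**Step 5: what the contrast in change can detect.** With 21 per group its power is 16% for a true difference of 0.3 SD of change, 35% for 0.5 SD, and 80% only at 0.89 SD.

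**The case against.** A reader might infer that practice alone can produce the hypothesised result. The documents do not support that. The hypothesis is an association with migraine improvement. Non-responders sit the same tests on the same schedule and so form an internal repeat-tested comparator. The plan names group comparisons on cognitive measures, and an equal practice gain creates no difference in them. Practice can mimic the association only if two separate within-group results are set against each other (step 2), or if the practice gain itself differs by response.

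Other strong readings also fail:

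- **Silence on practice.** That no practice run is given, that no alternate forms are used, or that controls were tested only once is inferred from silence. The test descriptions are short: "Subjects will complete the standardized worksheets of Trails A and B" does not settle the question of alternate forms.
- **A pooled test.** One might quote rejection rates for all 42 evaluable patients, but no pooled cognitive pre-post test is specified.
- **A declared success.** The plan sets no success rule for cognition, and these changes are to be explored.
- **n-back.** The missing control data are disclosed, control comparisons are made where data exist, and the hypothesis does not name n-back. Whether Trails control data exist is not stated.

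What remains is that the stated within-group tests do not separate practice from treatment, that the between-group timing described is post-treatment, and that no contrast in change from baseline is named, although the baseline scores will be in hand.

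**Conclusion.** The point holds as a gap in specification, not as a flaw that invalidates the cognitive aim. Under a practice-only shift of 0.2 to 0.5 SD of change, within-group significance at n = 21 occurs in 14% to 59% of trials, and the misleading split between responders and non-responders in 12% to 24%. A direct contrast of change stays at about 5%.

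These figures rest on an assumed practice effect, equal in the two groups, and on 21 patients in each. If practice gain differs by response status, the contrast in change does not remove it. Even with the fix, the contrast speaks to association with response, which is what the hypothesis states, and not to the effect of erenumab against no treatment.

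For n-back, the plan's own statement means that change can be reported but movement toward normal cannot. Cognition is a secondary, exploratory outcome, and the primary analysis of pain-induced activation is unaffected.

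**What to change.** 1. In Analysis Plans, Specific Aim #1, base any cognitive claim on the responder versus non-responder difference in change from baseline: either the group-by-time term in the mixed model or the post-treatment score adjusted for baseline. Name one in advance, because the two can disagree when non-randomised groups differ at baseline.
2. Report within-group cognitive change as descriptive only, and do not infer an association by setting separate within-group p-values side by side.
3. In the Summary and in Analysis Plans, limit normalization to measures with healthy-control data. Report n-back as change only, and state whether Trails control data exist.

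The cost is a few sentences, with no new visits, data or patients. The contrast is less precise than the within-group test (step 5), so a null result will say little, and the n-back claim becomes narrower. An unscored practice run before the baseline tests is optional and is not needed for this fix.
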